APPENDIX 2. MULTIPLE IMPUTATION WASHOUT MODEL

A multiple imputation washout model will be utilized for the primary efficacy analysis of the percentage change in LDL-C from baseline to Day 510 endpoint. The washout model can be thought of as a modified control-based Pattern-Mixture Model (PMM) that will be used to explore the possibility of data missing not at random (MNAR) for subjects who discontinued the study early. For subjects who discontinued the study early, their missing values will be imputed under the assumption that their outcome would be similar to those in the placebo group with similar background characteristics. For subjects in the inclisiran group only missing Day 510 values will be imputed. For subjects in the placebo group their missing values over all visits after early termination will be imputed based on the missing at random (MAR) assumption. Multiple imputation will be used to account for uncertainty in the imputation process and results from the imputed datasets will be combined using Rubin's method. Further details are provided below.

Windowing will be performed first (see [Section 6.3.3](#)) and any missing data will be imputed using the following steps.

The covariates and baseline characteristics which can be predictive of the response for the inclisiran group will be included in a multiple imputation procedure (SAS PROC MI) and will include the following:

- Baseline value of efficacy measurement (continuous)
- Observed value of efficacy measurement at Day 510 from the placebo group (continuous)
- Current use of statins or other lipid-modifying therapies (categorical)

The covariates and baseline characteristics which can be predictive of the response for the placebo group will be included in a multiple imputation procedure (SAS PROC MI) and will include the following:

- Baseline value of efficacy measurement (continuous)
 - Observed value of efficacy measurement at Day 90 (continuous)
 - Observed value of efficacy measurement at Day 150 (continuous)
 - Observed value of efficacy measurement at Day 270 (continuous)
 - Observed value of efficacy measurement at Day 330 (continuous)
 - Observed value of efficacy measurement at Day 450 (continuous)
 - Observed value of efficacy measurement at Day 510 (continuous)
 - Observed value of efficacy measurement at Day 540 (continuous)
 - Current use of statins or other lipid-modifying therapies (categorical)
1. Intermittent missing data in the placebo treatment group will be imputed using MCMC methods, assuming MAR. SAS PROC MI will be utilized for this step using the MCMC impute=monotone option. A total of 100 datasets will be created. These datasets will be utilized in Step #2.

2. The remaining missing values in the placebo group with a monotone missing data pattern will be imputed in this step. Missing data will be imputed assuming data are MAR. Only subjects in the placebo group will be utilized in this step. SAS PROC MI will be used to impute missing values utilizing the monotone reg option. This will be performed for the 100 datasets. After this step, the 100 datasets will be fully imputed for the placebo treatment group. These datasets will be utilized in Step #3.
3. The missing values at Day 510 in the inclisiran group will be imputed in this step. Control-based PMM imputation will be performed. With this imputation model, the missing efficacy measurements in the inclisiran group will not be constructed from the observed data in the inclisiran group but rather from the observed and imputed data in the placebo group at Day 510. Baseline data will also be utilized in the imputation. The MNAR statement in SAS PROC MI will be used to impute missing values. This will be performed for the 100 datasets. After this step, the 100 datasets will be fully imputed.
4. A total of 100 fully imputed datasets will be created (M=100). Since multiple imputation is a stochastic method, slight differences in output can be expected for different initial states of the random number generator. The seed numbers will be identified in the SAS programs to allow for reproducibility.
5. After the missing data imputation is completed using the above steps, absolute change/percentage change values will be calculated in each of the imputed datasets at each visit.
6. These 100 datasets will be analyzed using ANCOVA models with fixed effects of treatment group and current use of statins or other lipid-modifying therapies at baseline (yes or no) and baseline LDL-C as a covariate for the percent change of LDL-C from baseline to Day 510 primary efficacy endpoint.
7. Treatment effects (difference in LS means between treatments) from these 100 analyses will then be combined using Rubin's Method via SAS PROC MIANALYZE procedure for each endpoint.

APPENDIX 3. CONTROL-BASED PATTERN MIXTURE MODEL

A control-based Pattern-Mixture Model (PMM) will be used to explore the possibility of data missing not at random (MNAR) for subjects who discontinued the study. For subjects who discontinued the study without any further follow-up data, their missing values after study discontinuation will be imputed under the assumption that their outcome would be similar to those in the placebo group with similar background characteristics. For subjects who did not discontinue the study, their intermittent missing values will be imputed based on the MAR assumption. Multiple imputation will be used to account for uncertainty in the imputation process and results from the imputed datasets will be combined using Rubin's method. Further details are provided below.

Windowing will be performed first (see [Section 6.3.3](#)) and any missing data will be imputed using the following steps.

The covariates and baseline characteristics which can be predictive of the response will be included in a multiple imputation procedure (SAS PROC MI) and will include the following:

- Baseline value of efficacy measurement (continuous)
 - Observed value of efficacy measurement at Day 90 (continuous)
 - Observed value of efficacy measurement at Day 150 (continuous)
 - Observed value of efficacy measurement at Day 270 (continuous)
 - Observed value of efficacy measurement at Day 330 (continuous)
 - Observed value of efficacy measurement at Day 450 (continuous)
 - Observed value of efficacy measurement at Day 510 (continuous)
 - Observed value of efficacy measurement at Day 540 (continuous)
 - Current use of statins or other lipid-modifying therapies (categorical)
1. Intermittent missing data will be imputed using MCMC methods, assuming MAR, within each treatment group. SAS PROC MI will be utilized for this step using the MCMC impute=monotone option. A total of 100 datasets will be created. These datasets will be utilized in Step #2.
 2. The remaining missing values with a monotone missing data pattern will be imputed in this step. Control-based PMM imputation will be performed. With this imputation model, the missing efficacy measurements in the inclisiran group will not be constructed from the observed data in the inclisiran group but rather from the observed data in the placebo group. We will also use this model to impute missing efficacy measurements in the placebo group. The MNAR statement in SAS PROC MI will be used to impute missing values under the aforementioned assumptions. This will be performed for the 100 datasets. After this step, the 100 datasets will be fully imputed.
 3. A total of 100 fully imputed datasets will be created (M=100). Since multiple imputation is a stochastic method, slight differences in output can be expected for different initial states of the random number generator. The seed numbers will be identified in the SAS programs to allow for reproducibility.

4. After the missing data imputation is completed using the above steps, absolute change/percentage change values will be calculated in each of the imputed datasets at each visit.
5. These 100 datasets will be analyzed using the MMRM described in [Appendix 1](#) for the co-primary efficacy endpoints and key secondary efficacy endpoints.
6. Treatment effects (difference in LS means between treatments) from these 100 analyses will then be combined using Rubin's Method via SAS PROC MIANALYZE procedure for each endpoint.

APPENDIX 4. CRITERIA FOR POTENTIALLY CLINICALLY SIGNIFICANT AND CLINICALLY SIGNIFICANT ABNORMAL LABORATORY TESTS

Hemoglobin A1C criteria is explicitly stated in the table below.

All other criteria are met when both of the following occur:

- Post-baseline values meet the thresholds below
- Baseline values or any previous post-baseline values do not meet the thresholds below

Parameter	Unit	Lower Boundary	Upper Boundary
Hematology			
Hematocrit	%	$\leq 0.8 \times \text{LLN}$	N/A
Hemoglobin	g/dL	$\leq 10 \text{ g/dL}$	N/A
Platelet Count	$10^9/\text{L}$	$\leq 75^*$	$\geq 700^*$
White Blood Cell Count	$10^9/\text{L}$	≤ 2.8	≥ 16
Serum Chemistry			
Alanine Aminotransferase (ALT/SGPT)	U/L	N/A	$>1 \text{ and } \leq 3 \times \text{ULN}$
Alanine Aminotransferase (ALT/SGPT)	U/L	N/A	$>3 \text{ and } \leq 5 \times \text{ULN}^*$
Alanine Aminotransferase (ALT/SGPT)	U/L	N/A	$>5 \text{ and } \leq 10 \times \text{ULN}^*$
Alanine Aminotransferase (ALT/SGPT)	U/L	N/A	$>10 \text{ and } \leq 20 \times \text{ULN}^*$
Alanine Aminotransferase (ALT/SGPT)	U/L	N/A	$>20 \times \text{ULN}^*$
Alkaline Phosphatase	U/L	N/A	$>2 \times \text{ULN}^*$
Aspartate Aminotransferase (AST/SGOT)	U/L	N/A	$>1 \text{ and } \leq 3 \times \text{ULN}$
Aspartate Aminotransferase (AST/SGOT)	U/L	N/A	$>3 \text{ and } \leq 5 \times \text{ULN}^*$
Aspartate Aminotransferase (AST/SGOT)	U/L	N/A	$>5 \text{ and } \leq 10 \times \text{ULN}^*$
Aspartate Aminotransferase (AST/SGOT)	U/L	N/A	$>10 \text{ and } \leq 20 \times \text{ULN}^*$
Aspartate Aminotransferase (AST/SGOT)	U/L	N/A	$>20 \times \text{ULN}^*$
Creatine Kinase (CK)	U/L	N/A	$>1 \text{ and } \leq 3 \times \text{ULN}$
Creatine Kinase (CK)	U/L	N/A	$>3 \text{ and } \leq 5 \times \text{ULN}$
Creatine Kinase (CK)	U/L	N/A	$>5 \times \text{ and } \leq 10 \times \text{ULN}^*$
Creatine Kinase (CK)	U/L	N/A	$>10 \text{ and } \leq 20 \times \text{ULN}^*$
Creatine Kinase (CK)	U/L	N/A	$>20 \times \text{ULN}^*$
Hemoglobin A1C	%	N/A	$\geq 6.5\% \text{ and } \geq 0.5\% \text{ change from baseline}$
Serum Creatinine	mg/dL	N/A	$\geq 50\% \text{ increase from Baseline or } >2 \text{ mg/dL}^*$
Total Bilirubin	mg/dL	N/A	$>2 \times \text{ULN}^*$

LLN: Lower limit of the standard reference (normal) range; ULN: Upper limit of the standard reference (normal) range; N/A is Not Applicable.

*Clinically significant laboratory boundaries.

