#### 10.4.4.2. Laboratory Tests

Laboratory values will be summarized by treatment group, including changes and percent changes from baseline at each time point. Analyses will also be performed for each laboratory parameter by treatment group for incidence rates of both potentially clinical significant (PCS)/clinically significant (CS) values for subjects without PCS/CS value at baseline.

Numerical values of laboratory parameters from different local laboratories with different units and normal ranges will be converted to the conventional units and normalized to a standard set of reference/normal ranges. The normalization process will be performed and separated by each of the laboratory parameters. A shift analysis by normal range will be done which counts the number of patients with a low, normal or high value at baseline and a low, normal or high value post baseline.

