6.4.8.2. Laboratory Tests

Laboratory values will be summarized by treatment group, including the observed value, changes and percent changes from baseline at each time point.

A shift analysis using the normal range (except for eGFR and HbA1c) will be done which counts the number of subjects with a low, normal or high value at baseline and a low, normal or high value post baseline.

The following ranges will be used for eGFR and HbA1c

- For eGFR, the categories will be Severe = <30 mL/min/1.73m²; Moderate = ≥ 30 to <60 mL/min/1.73m²; Mild = ≥ 60 to <90 mL/min/1.73m²; and Normal = ≥ 90 mL/min/1.73m².
- For HbA1c, the categories will be $\leq 5.6\%$, $\geq 5.7\%$ to $\leq 6.4\%$, and $\geq 6.5\%$.

The baseline and worst post-baseline value will be utilized for the shift tables. Note that the shift table dealing with the fasting glucose parameter will require the lab sample to be taken while fasting. Samples taken while the subject was not fasting will not be analyzed.

The number and percentage of subjects with potentially clinically significant (PCS) laboratory values and clinically significant (CS) laboratory values (refer to [Appendix 4](#) for the criteria) will be summarized by treatment group. Hemoglobin A1c criteria is explicitly stated in Appendix 4. All other PCS and CS criteria are met when both of the following occur:

- Post-baseline values meet the thresholds listed in Appendix 4
- Baseline values or any prior post-baseline values do not meet the thresholds listed in Appendix 4

PCS chemistry laboratory values will also be classified as follows:

- Abnormal baseline:
 - Non HbA1c: >1 and $\leq 3x$ ULN at baseline and >1 and $\leq 3x$ ULN at final visit
 - HbA1c: $\geq 6.5\%$ at baseline and $\geq 6.5\%$ and $\geq 0.5\%$ change from baseline at final visit
- Elevated further:
 - Non HbA1c: >1 and $\leq 3x$ ULN at baseline or post baseline and becoming $> 3x$ ULN post baseline
- Final visit:
 - Non HbA1c: >1 and $\leq 3x$ ULN at final visit only but not at baseline or previous visits
 - HbA1c: $\geq 6.5\%$ and $\geq 0.5\%$ change from baseline at final visit only but not at baseline or previous visits
- Persistently elevated:
 - Non HbA1c: >1 and $\leq 3x$ ULN at a post baseline visit and remains >1 and $\leq 3x$ ULN until final visit
 - HbA1c: $\geq 6.5\%$ and $\geq 0.5\%$ change from baseline at a post baseline visit and remains $\geq 6.5\%$ and $\geq 0.5\%$ change from baseline until final visit
- Resolved:

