- Non HbA1c: >1 and ≤ 3 x ULN at baseline or post baseline, resolved to $<$ ULN at any post baseline visit, and remaining $<$ ULN at final visit
- HbA1c: $\geq 6.5\%$ at baseline or $\geq 6.5\%$ and $\geq 0.5\%$ change from baseline for post-baseline, resolved to $<6.5\%$ and $<0.5\%$ change from baseline at any post baseline visit, and remaining $<6.5\%$ and $<0.5\%$ change from baseline at final visit

Separate listings of all subjects with PCS and CS laboratory values will be presented. Subjects will appear once per lab parameter but may appear under multiple lab parameters. The worst post-baseline value will be utilized in the analyses.

The number and percentage of subjects satisfying Hy's Law will also be tabulated by treatment group based on the following lab findings:

- Any elevated post-baseline aminotransferases defined as:
 - ALT > 3 x ULN or
 - AST > 3 x ULN
- Elevated post-baseline serum total bilirubin (TBL) > 2 x ULN and serum alkaline phosphatase (ALP) levels < 2 x ULN

Subjects must meet all of the criteria listed above at the same time point and have normal lab parameters (ALT, AST, TBL) at baseline to be considered a Hy's Law case.

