8. CHANGES TO ANALYSES SPECIFIED IN THE PROTOCOL

The following items were changed between the final version of the protocol and the final SAP.

- Primary efficacy endpoint analyses were modified per FDA feedback.
- Imputation methods were modified per FDA feedback.
- Subgroup analyses were added for select variables.
- A secondary efficacy endpoint was renamed from mean maximum percent change to maximum percent change.
- The exploratory endpoint, proportion of subjects in each group with any LDL-C reduction from baseline at any visit (responders), was added
- Identification of PCS/CS laboratory values were modified.

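### The PCS/CS rule for ALT, AST and CK has no direction clause, so a fall to a lower band still above ULN can be counted as a new abnormality

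*SAP*

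**What the plan says.** Appendix 4 of the SAP gives ALT, AST and CK five rows each: >1 to <=3, >3 to <=5, >5 to <=10, >10 to <=20, and >20 x ULN. Only the last has no upper bound. For ALT and AST every row above 3 x ULN is marked clinically significant (CS). For CK the CS mark starts above 5 x ULN.

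HbA1c has its own criterion. For every other parameter two conditions must hold together. The first is "Post-baseline values meet the thresholds below". The second is "Baseline values or any previous post-baseline values do not meet the thresholds below". Section 6.4.8.2 repeats the second almost unchanged: "Baseline values or any prior post-baseline values do not meet the thresholds listed in Appendix 4". It adds, in the paragraph on listings, "The worst post-baseline value will be utilized in the analyses".

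Three other places bear on the meaning:

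- Section 6.4.8.2 sorts PCS chemistry values into classes. One of them, *Elevated further*, covers a value >1 to <=3 x "ULN at baseline or post baseline and becoming" more than 3 x ULN afterwards.
- Protocol Section 10.4.4.2 plans incidence rates "for subjects without PCS/CS value at baseline".
- SAP Section 8 lists among the changes from the protocol: "Identification of PCS/CS laboratory values were modified". It does not say how.

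**The concern.** A new abnormality on treatment should mean that the value got worse. When a band has an upper bound, a baseline value can lie outside it for two opposite reasons: it was lower, or it was higher. The second condition asks only whether baseline was outside, so it treats the two alike. An improvement can then enter the table as a new finding.

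The rule also leaves open what the baseline value is compared with. If it is the same row, falls are counted. If it is any row of that parameter, a subject with a slightly raised baseline can never be counted, however high the later value. Two programmers working from this text could produce different tables.

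At stake are the counts and listings of new liver-enzyme and muscle-enzyme abnormalities. They are descriptive, but readers will use them to judge hepatic and muscle safety.

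**Working it through.** The plan states no figure to reproduce, so the check enumerates the rule.

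**Inputs.** The five bands and the two conditions come from Appendix 4, and the use of the worst post-baseline value from Section 6.4.8.2. Adding a category for <=1 x ULN gives six categories at baseline and six for the worst post-baseline value: 6 x 6 = 36 pairs. Of these, 6 x 5 / 2 = 15 go up, 15 go down and 6 stay the same.

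**Same-row reading.** Flag if the worst value is in band *k* and baseline is not in band *k*.

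- All 15 upward shifts are flagged and none of the 6 unchanged pairs.
- Of the 15 downward shifts, 5 end at or below ULN and meet no row. The other 15 - 5 = 10 end in a band above ULN, and all 10 are flagged.
- Example: baseline CK 4 x ULN is outside >1 to <=3, and a worst later value of 2 x ULN is inside it. Both conditions hold, so the subject is a new PCS case. Using the worst value does not help, because 2 x ULN is this subject's worst value.

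**Any-row reading.** Flag if the worst value is in a band and baseline is in none of them.

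- No downward shift is flagged.
- Only the 5 upward shifts that start at or below ULN are flagged. The other 15 - 5 = 10 are lost. Example: baseline 1.2 x ULN rising to 25 x ULN appears in no row.

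**Direction-aware rule.** Flag if the worst value is in band *k* and baseline is at or below the lower limit of band *k*.

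| Rule | Upward flagged (of 15) | Downward flagged (of 15) | Unchanged flagged (of 6) |
|---|---|---|---|
| Same row, as written | 15 | 10 | 0 |
| Any row, as written | 5 | 0 | 0 |
| Same row, baseline at or below lower limit | 15 | 0 | 0 |

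These are counts of category pairs, not of subjects.

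**Where the 10 falls land.** By receiving row, from the lowest up, there are 4, 3, 2 and 1. For CK the two lowest rows are PCS only, so 4 + 3 = 7 of the 10 are not clinically significant. The other 3 need a baseline above 10 x ULN. For every parameter, all 10 start from a baseline above 3 x ULN. Exclusion criterion 7 (Protocol Section 4.3) makes that uncommon for ALT and AST, because it bars unexplained, repeat-confirmed values above 3 x ULN at screening. It is not impossible: an explained or unconfirmed rise is not barred, and baseline is the latest pre-dose value (SAP Section 6.3.3). Neither Section 4.2 nor 4.3 of the protocol sets a CK limit.

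**Earlier post-baseline values.** The second condition also names these without saying how they enter. Applied row by row at each visit, a course of 0.8, 4, 2 x ULN fills two rows (>3 to <=5, then >1 to <=3 on the way down). Using only the worst value leaves one.

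**The case against.** **The any-row reading is not what the SAP means.** *Elevated further* is a class of PCS values that includes subjects with a mildly raised baseline. It has little use for them if such a baseline bars them from being PCS. Section 8 also says the SAP departs from the protocol on this point, so Protocol Section 10.4.4.2 is weak support for the any-row meaning. This stands, and it makes the same-row reading the likelier one. It does not close the question, because Section 8 does not state the change and neither statement of the rule names the row.

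**A reader might infer that many severe rises will be missing from the safety tables.** The documents do not support that. It would need the less likely reading, and it would need a distribution of baseline values that the documents do not give.

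**The same-row error is narrow.** A false flag needs a baseline above 3 x ULN and every later value in a lower band. For ALT and AST such baselines are uncommon, and for CK most of the receiving rows are PCS only. This stands.

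**Other displays are sound.** The Hy's Law count requires normal ALT, AST and bilirubin at baseline and does not use Appendix 4. The shift table shows 4 to 2 x ULN as high to high, not as new. Both are true, but neither corrects the PCS counts, and the listings of PCS and CS subjects inherit the rule. The shift table would also show 1.2 to 25 x ULN as high to high.

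**A reader might infer bias between the arms.** Randomization balances raised baselines in expectation, and nothing in the documents shows that false flags would favour one arm.

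**Conclusion.** The point holds as a defect of definition in descriptive safety tables. On the likelier same-row reading, every fall to a lower band that is still above ULN is counted as a new PCS or CS value: 10 of the 15 downward category shifts. In practice this concerns mainly CK, and mostly rows that are not clinically significant. On the less likely any-row reading, 10 of the 15 upward shifts would go uncounted.

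The conclusion rests on the literal wording and on the worst-value sentence applying to the counts as well as to the listings. It affects only the banded parameters, ALT, AST and CK. The number of subjects misclassified cannot be computed, because any figure would reflect an assumed baseline distribution. No efficacy endpoint, hypothesis test or Hy's Law count is touched.

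**What to change.** In Appendix 4, keep the bands and state that, for ALT, AST and CK, each subject is classified by the worst post-baseline value, and the band containing it is flagged only if the baseline value is at or below that band's lower limit. Say that the comparison is with the same row. Then 4 to 2 x ULN is not flagged, and 1.2 to 25 x ULN is flagged at >20 x ULN. State the same rule in Section 6.4.8.2, and say how earlier post-baseline values are treated.

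Open thresholds (>1, >3, >5, >10, >20 x ULN) with a same-row baseline condition are an alternative, but each row then has a different at-risk set. The rows are not nested and must not be subtracted to give band counts. The subject going from 1.2 to 25 x ULN is not counted at >1 but is counted at >3, so the >1 row minus the >3 row gives 0 - 1 = -1.

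The cost is a few sentences and a small change to one derivation. No new data are needed.
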